## **14.0 Withdrawal of Subjects\***

*14.1* A participant may be withdrawn from the study without their consent in order to maintain the integrity of the data (e.g., participant is not following procedures or is deliberately providing false information).

*14.2* If a participant is withdrawn from the study without their consent, we will take the following steps: a) We will inform the participant in writing of the decision including an explanation for the decision; b) We will notify the IRB of our decision to withdraw the participant.

*14.3* If subjects withdraw, their information will be kept and labeled as withdrawn. These withdrawn subjects will not be contacted further. If a subject chooses to withdraw from the study, we will continue to utilize all data collected up to the point of subject withdrawal. It states in the informed consent document that subjects are free to withdraw at any point during the study. Some subjects may decide to withdraw because they no longer wish, or have time, to do the follow-up interviews. From our previous genetic counseling studies, approximately 15% of participants withdraw prior to completion of the study. The majority of those who withdraw usually do so because they no longer want to complete study assessments. We will track withdrawals and report them in study findings. There are no biomedical safety implications from this type of partial withdraw.

## **15.0 Risks to Subjects\***

*15.1* Risks associated with participating in this study fall into three categories. First is the risk associated with completing the study surveys. There is a low risk of adverse psychological reactions to the study surveys. Asking men with prostate cancer to reflect on their/their family's cancer risks, their cancer screening behaviors, and their reactions to genetic testing could generate anxiety for some

individuals. However, because these individuals agreed to study participation, these are likely topics that they are willing to discuss. It is possible that persons likely to be overly concerned or harmed by the experience of discussing cancer risk will choose not to participate, although our prior data show that we have recruited participants reporting a broad continuum of cancer worry and risk perception with no adverse consequences. Thus, we consider this to be a minimal risk to patients.

Second, there may be modest risks associated with participation in genetic education or genetic counseling. Participants may experience mild psychological distress regarding their risk for carrying a PV in a cancer risk gene and the potential increase in risk for cancer in the participant and his family members.

Our plan for addressing adverse psychological reactions is comprehensive and is modeled on our current approach within the clinical cancer genetics program at LCCC ([name], Medical Director; [name] Counseling Director). First, any participants who report high levels of distress during a study contact or on a study survey instrument will be referred for follow-up psychological assessment to a mental health provider. Second, all participants who undergo genetic testing and receive a PV or VUS result will have an individual genetic counseling disclosure session with a board-certified genetic counselor. As part of this session, the counselor will assess participant distress and coping difficulties. Specific follow-up referrals will be made for participants exhibiting psychosocial difficulties. Because attention to psychological issues has been a longstanding component of comprehensive genetic counseling, it is anticipated that psychological injury will be infrequent. In fact, quite to the contrary, considerable research documents beneficial psychosocial effects of counseling. Even for patients who receive positive test results, there is little evidence to suggest adverse psychological effects.

There may also be risks for ST participants who proceed directly to genetic testing without an individual genetic counseling session. However, we believe that the risk to these participants is low for several reasons. A) In community practice approximately 50% of individuals who receive cancer genetic testing do so without any pre-test genetic education or counseling; B) All participants who are randomized to ST will have the option to request individual telephone genetic counseling free of charge through the study; C) All individuals who proceed to genetic testing and are found to carry a PV or VUS result will receive their test results in the context of a standard genetic counseling disclosure session with a board-certified genetic counselor; D) The population in the current study all meet guidelines for genetic referral. There are insufficient counseling resources to retrospectively contact and counsel all prostate cancer survivors who meet criteria for genetic testing. Thus, from a clinical perspective, it is critical to develop effective and efficient genetic education approaches to foster informed genetic testing decisions. Finally, the personal health implications of a positive genetic test result in men are much less pronounced and immediate than in women. Thus, the risk of adverse psychosocial outcomes (already low in women who undergo testing) is quite low.

For all patients who choose to proceed with genetic testing, there may be additional risks. Although participants will neither be encouraged nor discouraged from undergoing testing as part of this study, for those who choose to pursue testing, additional potential risks include insurance and employment discrimination and the small possibility of incorrect or inaccurate test results. The ST materials contain information about laws protecting against genetic discrimination, and the standard clinical laboratory consent form outlines the small possibility of incorrect or inaccurate test results.

Finally, in addition to psychosocial risks that may be associated with genetic counseling, there may also be risks related to confidentiality and loss of privacy should an unauthorized third-party learn that the participant received genetic counseling and testing.

## **16.0 Potential Benefits to Subjects\***

*16.1* The potential benefit of this study to the participants is an increased knowledge of genetic testing for cancer susceptibility and a better understanding of the implications for treatment, screening, and risk reduction in men who carry a PV and their family members.

## **17.0 Data Management\* and Confidentiality**

*17.1* Data Analysis: We will characterize participants by comparing them to decliners on key demographic and clinical variables derived from the EMR. After performing univariate analysis on dependent variables, we will apply any needed normalizing or variance stabilizing transformations. We will follow Consort guidelines for Intent-to-Treat analyses (ITT). We will compare groups at baseline with  $\chi^2$  and t-tests and will include covariates that are associated with group ( $p < 0.10$ ) in our final models.

**Aim 1: Evaluate the impact of Proactive Streamlined Education and Testing (ST) vs. Usual Care (UC) on genetic testing.** Analysis: H1.1: Patients randomized to ST will be more likely to complete genetic testing compared to UC. We will use logistic regression to test this hypothesis. After entering significant covariates, we will add intervention arm to test the overall intervention effect. H1.2: Participants randomized to ST will make better informed genetic testing decisions (characterized by high knowledge, risk comprehension and positive attitudes) compared to UC. Using multiple regression, we will enter control/confounding variables and intervention to test the impact of group on our informed decision making outcomes (knowledge, testing attitudes, risk comprehension). H1.3: Few patients in the ST arm will opt for traditional genetic counseling prior to testing. We will conduct descriptive analyses describing the proportion of ST participants who opt for genetic counseling vs. proceed directly to testing vs. opt against testing.

**Aim 2: Evaluate patient satisfaction and psychosocial outcomes in ST vs. UC.** Analysis: H2.1: Compared to UC, those randomized to ST will be more satisfied with their genetic testing decision and will have less decisional regret. After identifying baseline confounders of each outcome, we will generate linear regression models in which we enter: 1) confounders; 2) genetic test result (dummy

coded to generate comparisons of carriers vs. non-carriers and non-carriers vs. untested); 3) group assignment. In the event that we have an insufficient number of PV carriers for these analyses, we will categorize test result into two levels (tested vs. untested) and evaluate results among PV carriers more descriptively. Results of Aim 2 analyses will be primarily focused on generating effect size estimates for our planned trial of newly diagnosed prostate cancer patients.

**Aim 3: Evaluate the impact of ST vs. UC on uptake of cascade testing in unaffected family members.** In exploratory analyses designed to provide effect size estimates for our planned R01, we will use t-test to compare the ST to UC on the number of relatives of PV carriers who undergo cascade genetic testing.

**Power:** Power estimates are for 2-tailed tests ( $\alpha=.05$ ). The study is powered based on our primary outcome of patient genetic testing uptake. We expect no attrition since data will be abstracted from clinic records. With no relevant studies on which

Table 2. Sample Size Calculation			
	ST Uptake		
UC Uptake	.40	.45	.50
10%	39	25	20
15%	49	36	27
20%	81	54	39

to base our effect sizes for this pilot study, Table 2 displays the necessary sample size (per group) to obtain 80% power for a range of potential clinically significant effects on test uptake (40%-50% for ST; 10%-20% for UC). Based on this analysis, we will enroll 120 participants in order to attain 80% power to detect a clinically meaningful difference between 20% in UC and 45% in ST. For our secondary outcomes, a sample size of 120 and 10% attrition at 3-months (n=108 in final sample) will provide  $> 80\%$  power to detect medium sized effects of  $d=.54$  SDs on our secondary outcomes (e.g., decisional conflict, patient satisfaction). This effect size is well within the range that we have seen in previous studies and represents an effect that is generally considered to be clinically significant.

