Recruitment. Working with our clinical collaborators and the Survey, Recruitment and Biospecimen Collection Shared Resource (SRBSR) will obtain contact information of potentially eligible patients from clinical databases and/or the EMR. We will mail an introductory letter describing the study (from the study MPIs and the patient's physician), opt-out postcard/phone number, informed consent document and a print version of the baseline survey to all potentially eligible participants. We will also email electronic versions of these materials for patients who prefer to complete them online. Two-weeks following this mailing, an SRBSR research assistant (RA) will call patients who have neither opted out nor completed the baseline survey. For men who have not returned the consent document, we will use an IRB-approved verbal consent for completing the baseline survey and request return of the written consent prior to randomization. Following completion of print or electronic consent and the baseline survey, the RA will randomize participants. Men randomized to ST will be sent a priority mail packet with detailed genetic testing educational material. Men randomized to UC will be mailed a letter informing them that they meet guidelines for genetic counseling and provided with contact information to schedule a genetic counseling appointment with a LCCC genetic counselor.

Randomization. Following completion of the baseline survey and consent document, an RA will randomize participants via computer-generated random numbers in blocks of 8 and a ratio of 1:1. Participants will be notified of their random assignment via letter and email.

**Assessments.** We will administer baseline (T0) and 2- to 3-month (T1) follow-up telephone/electronic surveys. Genetic testing uptake will be assessed via clinical records and basic clinical and demographic information abstracted from the EMR. See Table 1 for assessment instruments and schedule of administration.

Table 1. Measures		T0	T1
Variables	Measures		
Covariates/Background Variables	Demographics, clinical variables, family history (EMR/survey)	X	
Health Literacy	Brief Health Literacy Screening Tool	X	
Genetic Test Uptake	Study Records		X
Knowledge/Risk Comprehension	Genetic Knowledge Scale and Perceived Mutation Risk.	X	X
Attitudes	Adapted version of the Multimodal Measure of Informed Choice (MMIC), Fatalism, Medical Mistrust Index	X	
Decision Regret	Decisional-Regret Scale.		X

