Decision Satisfaction	Satisfaction with Decision Scale.		X
Distress	Cancer distress: PROMIS Anxiety and Depression; Genetic testing distress MICRA.	X	X
Quality of Life/Functional Status	PROMIS Physical Function and Social Function Short Forms	X	X
Cascade Testing	Number of relatives who have proceeded with genetic testing.		X

**Streamlined Testing (ST) Intervention.** Men randomized to ST will be sent a priority mail packet with the ST print education materials and information on how to proceed with genetic testing. ST participants will have the option of proceeding directly to genetic testing or scheduling a telephone genetic counseling session. The content of the ST intervention is described in section 5.0 above.

**Usual Care (UC).** After completion of the baseline survey, UC participants will be sent a letter from their physician indicating that they meet eligibility criteria for genetic testing, recommending that they schedule genetic counseling and providing a contact telephone number to schedule their session. Patients may opt for free telephone genetic counseling.

**Genetic Testing.** Participants who choose to pursue genetic testing will be offered a standard clinical multigene panel of at least 40 genes, including *BRCA* and genes associated with potential differential diagnoses (e.g., Lynch syndrome). All testing will be performed by Invitae, a CLIA certified clinical lab not affiliated with the GLCCC. Invitae offers genetic testing free of charge to eligible prostate cancer patients (all study participants will be eligible for free genetic testing through Invitae). Prior to proceeding with genetic testing, participants will be required to sign and return a clinical genetic testing consent form, after which we will mail them an at-home DNA kit for saliva collection which will be returned directly to Invitae (shipping costs are pre-paid).

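### Covariates for the final models, including the primary uptake model, are chosen by testing baseline differences between randomised arms at p<0.10 rather than fixed in advance for prognostic value

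*Combined protocol and SAP*

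**What the plan says.** Section 17.1 (Data Analysis) sets a general rule ahead of the separate aims. The arms are compared at baseline with chi-square and t-tests, and the analysts "will include covariates that are associated with group" at p<0.10 in the final models.

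The aims then describe adjustment in three ways:

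- **H1.1 (primary outcome, logistic regression):** "After entering significant covariates, we will add intervention arm to test the overall intervention effect". The text does not say what the covariates must be significantly related to. The general rule just above it is the natural reading.
- **H1.2:** "we will enter control/confounding variables and intervention to test the impact of group". The variables are not named.
- **Aim 2, H2.1:** "After identifying baseline confounders of each outcome, we will generate linear regression models". Neither the confounders nor a way of identifying them is given.

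Section 6.0 (Randomization) says the research assistant will "randomize participants via computer-generated random numbers in blocks of 8 and a ratio of 1:1". No stratification factors are stated, so the design does not fix an adjustment set either. Table 1 lists broad background categories and schedules the instruments. "Genetic Knowledge Scale and Perceived Mutation Risk" is taken at T0 and T1, as are the PROMIS measures. "Satisfaction with Decision Scale" and the regret scale are taken at T1 only.

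**The concern.** In a randomised trial a baseline significance test asks whether chance produced the difference, and the answer is already known. A p<0.10 screen on those tests says nothing about whether a covariate predicts uptake, which is what decides whether adjusting for it helps. Strong predictors that happen to be balanced are left out, and irrelevant variables that happen to be imbalanced are put in.

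Two things follow. First, the logistic odds ratio for arm changes in meaning when a prognostic covariate enters, even with no confounding. Under this rule the data decide which odds ratio is reported for the primary outcome. That matters for a pilot which, by Sections 2.0 and 3.0, is meant to supply preliminary efficacy data for a larger trial. Second, most of the power available from measured prognostic covariates goes unused. In linear models the test also becomes conservative when the covariate is prognostic.

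**Working it through.** **Inputs from the documents (Section 17.1, Power, and Section 6.0).** Two-sided alpha 0.05; uptake 20% in UC and 45% in ST; 120 enrolled, 60 per arm, no attrition for uptake; 108 analysed for secondary outcomes, 54 per arm, d = 0.54; screening threshold p<0.10. **Assumed:** prognostic strength, for which the documents give no figure, so a range is shown.

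**1. The plan's own figure.** Pooled-variance formula without continuity correction, with mean rate 0.325:

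n = [1.960 × √(2 × 0.325 × 0.675) + 0.842 × √(0.20 × 0.80 + 0.45 × 0.55)]² / 0.25² = (1.298 + 0.537)² / 0.0625 = 53.9, so 54 per arm.

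This matches Table 2. With 60 per arm, power is Φ[(0.25 × √60 − 1.298) / 0.638] = Φ(1.00) = 84.1%.

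**2. How often the screen admits something.** For k independent candidates the expected number admitted is 0.10k, and the chance of at least one is 1 − 0.9^k: 41% (k = 5), 65% (k = 10), 79% (k = 15), 88% (k = 20).

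**3. What the primary odds ratio means.** Marginal odds ratio = (0.45/0.55)/(0.20/0.80) = 3.27. Intercepts were solved so that average uptake stays at 20% and 45% with a standard-normal covariate in the model. The arm odds ratio conditional on that covariate is in the last column of the next table.

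**4. Power for uptake.** 60 per arm, one covariate, Wald test for arm, 20,000 simulated trials per setting. Type I error was simulated at 32.5% uptake in both arms.

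| Covariate OR per SD | Power, p<0.10 rule | Power, always adjusting | Difference (points) | Type I error, rule | Conditional OR for arm |
|---|---|---|---|---|---|
| 1 | 83.8% | 83.9% | 0.1 | 4.7% | 3.27 |
| 2 | 84.4% | 87.1% | 2.7 | 4.4% | 3.66 |
| 3 | 85.3% | 90.1% | 4.8 | 4.0% | 4.25 |
| 5 | 86.1% | 93.6% | 7.5 | 3.7% | 5.41 |

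Always adjusting has type I error of 4.9% to 5.0%. The standard error of the log odds ratio rises from about 0.42 unadjusted to 0.45, 0.48 and 0.53 for covariate odds ratios of 2, 3 and 5. The gain is therefore in power, because the conditional effect grows faster than its standard error, and not in a narrower interval on the log scale.

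**5. Power for continuous outcomes.** 54 per arm, d = 0.54, one covariate with correlation r to the outcome, 100,000 simulated trials per setting.

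| r | Power, p<0.10 rule | Power, always adjusting | Type I error, rule |
|---|---|---|---|
| 0 | 79.1% | 79.0% | 5.0% |
| 0.3 | 80.2% | 82.8% | 4.8% |
| 0.5 | 81.3% | 89.2% | 4.1% |
| 0.7 | 82.9% | 97.3% | 3.1% |

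As a check, always adjusting is close to a t-test at d/√(1 − r²). For r = 0.5 this is 0.54/0.866 = 0.62, with power 89.4%. For r = 0.3 and 0.7 the check gives 83.0% and 97.3%.

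**6. Several candidates at once.** A further simulation for uptake used ten independent candidates, three of them prognostic (log odds 0.5 to 0.8 per SD each), a likelihood-ratio test and 4,000 trials per setting. The rule picked about one covariate in ten regardless of prognostic value. At 20% versus 45%, power was about 85% unadjusted, 85% to 86% under the rule, and 88% to 93% with the three prognostic covariates fixed in advance.

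**The case against.** The strongest reply is that the harm is modest. Always adjusting for a known prognostic covariate is an ideal comparator. The natural benchmark is the unadjusted comparison behind the sample size, and against that the rule costs nothing: for uptake with a covariate odds ratio of 3, about 84% unadjusted and 85.3% under the rule; for a continuous outcome at r = 0.5, about 79% and 81.3%. The shift in the odds ratio is also small unless prognosis is strong: ln(3.66/3.27) = 0.11, about a quarter of the 0.42 standard error, and any one covariate enters only about 10% of the time. All of this stands. The power figures show a missed improvement, not a shortfall against the plan.

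It is also fair that H1.1 may mean covariates significantly associated with uptake. The simulations above would not then describe it, but selection would still be data-driven and its criterion undefined.

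Gains from a T0 score do not reach satisfaction or regret, the outcomes named in H2.1, because these are measured at T1 only. They apply to knowledge and risk comprehension and to the PROMIS scales. Aim 2 is also aimed mainly at effect-size estimation.

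Finally, a fixed list has a small technical cost. With three covariates and 20% uptake in both arms (24 expected events), type I error was 5.5% to 5.9% by likelihood-ratio test, against 4.7% to 4.9% by Wald test. This bears on how the fix is written and does not support keeping the screen.

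**Conclusion.** The concern holds. The stated rule lets chance imbalance decide the covariates in the final models, and no other text fixes them. The 80% power claim is sound and false positives are not inflated, so this is a worthwhile improvement and not a fatal flaw.

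Its size depends on prognostic strength, which is assumed throughout. With a non-prognostic covariate there is no material effect. With covariate odds ratios of 2 to 5 per SD, the primary odds ratio for the same true uptake ranges from 3.66 to 5.41 instead of 3.27, and about 3 to 8 points of power are left unused. For continuous outcomes with r from 0.3 to 0.7, the unused power is 2.6 to 14.4 points; the upper end needs a strongly correlated baseline score.

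**What to change.** Delete the p<0.10 screen and describe baseline balance without significance tests. Then specify in Section 17.1:

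- **Outcomes measured at T0 and T1** (knowledge and risk comprehension, PROMIS distress and function): regress T1 on arm and the outcome's own T0 value.
- **Outcomes without a T0 value** (uptake, satisfaction, regret): adjust for a short fixed list of baseline covariates already collected, chosen for expected prognostic value and named before unblinded data are seen.
- **Uptake:** keep the list to two or three, given 60 × 0.20 + 60 × 0.45 = 39 expected events under the planning rates (24 if uptake is 20% in both arms). Name the test for arm; the Wald test held its level in the three-covariate check. Beside the odds ratio, report the model-standardised risk difference (average predicted uptake under ST minus that under UC) with a 95% confidence interval. This is on the scale of the 20% versus 45% planning assumption, and its meaning does not change with the covariates.
- **H1.2 and Aim 2:** use the same fixed list wherever confounders are now mentioned.
- **Sensitivity analysis:** show the unadjusted result.

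Testing attitudes, an H1.2 outcome that Table 1 schedules at T0 only, fit neither group and need separate resolution.

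The cost is SAP wording, with no extra data. If the chosen covariates prove not to be prognostic there is little or no gain, and the simulated change in power is 0.1 point.

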We will enroll eligible prostate patients who were diagnosed between 2010 and 2019 and are being followed within radiation and medical oncology clinics at the MedStar Georgetown University Hospital (MGUH) and MedStar Washington Hospital Center (MWHC). In this initial pilot, we will not focus on newly diagnosed patients but instead will focus on patients who are being followed for a number of reasons: 1) Substantial numbers of patients who are currently being followed have now become candidates for genetic testing based on updated guidelines and 2) This will allow us to maximize our potential sample size within the one year framework of this grant, allowing us to obtain preliminary efficacy data in preparation for a planned multisite R01 study of newly diagnosed patients with high risk localized or metastatic disease. By providing information particularly salient to prostate cancer patients, reducing barriers to genetic testing and proactively facilitating genetic testing delivery, we expect that our proactive and streamlined approach will yield increased uptake of genetic testing. Our specific aims are:

- 1: **Evaluate the impact of ST vs. UC on genetic testing uptake.** *H1.1:* Patients randomized to ST will be more likely to complete genetic testing compared to UC. *H1.2:* Participants randomized to ST will make better informed genetic testing decisions (characterized by high knowledge, risk comprehension and concordance with attitudes) compared to UC. *H1.3:* Few patients in the ST arm will opt for traditional genetic counseling prior to testing.
- 2: **Evaluate patient satisfaction and psychosocial outcomes in ST vs. UC.** *H2.1:* Compared to UC, those randomized to ST will be more satisfied with their genetic testing decision and will have less decisional regret.
- 3: **Evaluate the impact of ST vs. UC on uptake of cascade testing in unaffected family members.** In exploratory analyses designed to provide effect size estimates, we will compare the arms on rates of genetic testing in relatives of patients found to carry a PV.

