## **6.0 Procedures Involved\***

6.1-6.4 The objective is to develop and pilot a novel streamlined approach to deliver genetic education and testing to the rapidly increasing number of prostate cancer patients who meet guidelines for genetic referral. Our streamlined genetic testing approach is designed to facilitate genetic education and testing for men with prostate cancer. The intervention will incorporate proactively delivered print educational materials in lieu of pre-test genetic counseling. The materials will increase awareness, expand access, provide

balanced information to foster informed genetic testing decisions and reduce barriers to facilitate the delivery of genetic testing. All men who are found to carry a PV or variant of uncertain significance (VUS) in a cancer risk gene will have an individual telephone genetic counseling disclosure session with a board-certified genetic counselor. We will recruit 120 prostate cancer survivors who meet clinical referral criteria. After a baseline survey, we will randomize participants to: ST vs. UC. Participants will complete a follow-up survey at 2-3-months post-randomization. Our primary outcome is genetic testing uptake.

Eligibility and Accrual. Men eligible for this study are currently being followed at MGUH or MWHC for either:

Metastatic prostate cancer;  
Gleason 7+ prostate cancer.

We will exclude patients who have had, or are already scheduled for genetic counseling or testing for *BRCA1* or *BRCA2* mutations. We will also exclude men who cannot participate in English and provide meaningful consent. We will recruit participants from medical and radiation oncology clinics at MGUH and MWHC. These clinics currently follow well over 1000 eligible patients.

Gender and Minorities. Participants will be adult men. Given the racial/ethnic breakdown of the clinics we are recruiting from. We expect that at least 30% of participants will be members of racial/ethnic minority groups.

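### H1.2 promises better informed testing decisions, but the planned analysis compares separate scores by arm and never links knowledge or attitude to whether the man tested

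*Combined protocol and SAP*

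**What the plan says.** Section 2.0 gives H1.2 as a hypothesis about the quality of testing decisions, "characterized by high knowledge, risk comprehension and concordance with attitudes". Section 17.1 restates it as "characterized by high knowledge, risk comprehension and positive attitudes", so concordance drops out. The analysis there is: "Using multiple regression, we will enter control/confounding variables and intervention to test the impact of group on our informed decision making outcomes". Three scores are named as those outcomes: "knowledge, testing attitudes, risk comprehension". The section sets no threshold for high knowledge, and whether the man tested enters neither the outcome nor the model.

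The neighbouring analyses do not fill the gap. H1.3 describes the choices of ST men without reference to knowledge. The Aim 2 models include test result, or tested against untested, but their outcomes are satisfaction and regret.

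On what the arms receive, section 6.0 says: "The intervention will incorporate proactively delivered print educational materials in lieu of pre-test genetic counseling". All ST men are sent that material. In the other arm, "UC participants will be sent a letter from their physician indicating that they meet eligibility criteria for genetic testing", and education follows only if the man schedules counseling. Table 1 places knowledge and risk comprehension at T0 and T1, uptake at T1, and attitudes (including the informed-choice instrument) at T0 only.

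**The concern.** An informed decision is a joint property: what the man knew, what he wanted and what he did. Three separate regressions on arm cannot recover it. Concordance cannot be read from a mean attitude score, and a mean knowledge score over all men does not say how informed the testers were.

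This matters because ST lets men bypass pre-test counseling. Section 15.1 acknowledges: "There may also be risks for ST participants who proceed directly to genetic testing without an individual genetic counseling session". The pilot is meant to support a larger trial of the same strategy. A favourable H1.2 is likely to be read as evidence that print informs men as well as counseling does. As planned, the analysis neither tests that nor describes it.

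There is also a data problem. Section 17.1 lists testing attitudes as an outcome, but Table 1 schedules no follow-up attitude score.

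**Working it through.** **Inputs from section 17.1.** Two-sided alpha 0.05; 60 men per arm; planned uptake 20% (UC) and 45% (ST), with ranges 10-20% and 40-50%; 10% survey attrition, leaving 54 per arm; d = 0.54 for secondary outcomes.

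**The plan's own figures.** The pooled two-proportion formula for 20% v 45% at 80% power gives 53.9, so 54 per group, as in Table 2. For d = 0.54 at 54 per arm, power is 80.1% (normal) or 79.4% (noncentral t), close to the stated figure of over 80%.

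**How many UC men are educated.** Share counseled = uptake / testing rate after counseling. Section 2.0 calls that rate high but gives no figure, so I assume 70-90%.
- 0.20/0.90 = 22% and 0.20/0.70 = 29%. With a rate anywhere from 50% to 100%, the share is 40% to 20%.
- At 10% uptake and a rate of 50% to 100%, it is 20% to 10%.
- Most UC men have had only the letter unless 0.20/rate reaches 0.50, that is, a testing rate of 40% or lower after counseling.

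**Does the mean contrast determine how informed the testers are?** The documents give no knowledge mean, SD or cut-off, so the following are assumptions, for illustration only: normal scores with SD 1; letter-only mean 0, counseled mean 1.0, ST mean 0.8; cut-off 0.5; 90% of counseled men test; no ST man is counseled.
- Mean difference = 0.8 - 0.222 x 1.0 = 0.578.
- The UC mixture has variance 1 + 0.222 x 0.778 = 1.173. Pooled SD = sqrt((1.173 + 1)/2) = 1.042.
- d = 0.578/1.042 = 0.55; power at 54 per arm is 81% (noncentral t).
- Counseled testers below the cut-off: Phi(0.5 - 1.0) = 31%.

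The share of ST testers below the cut-off depends on how testing relates to knowledge within ST, which the mean does not fix. Let propensity to test be normal, with testing above its 55th percentile, and let it correlate rho with the score:

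| rho | ST men tested and below cut-off | divided by 0.45 = share of ST testers |
|---|---|---|
| 0 | 17.2% | 38% |
| 0.3 | 12.6% | 28% |
| 0.5 | 9.4% | 21% |

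One mean difference, and therefore one H1.2 result, goes with ST testers who are less informed or more informed than counseled testers (31%).

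**All four cells (rho = 0, percent of randomised men).** UC letter-only men below the cut-off: Phi(0.5) = 69.1%. ST men below it: Phi(0.5 - 0.8) = 38.2%.

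| | UC | ST |
|---|---|---|
| Tested, adequate | 20 x 0.691 = 13.8 | 45 x 0.618 = 27.8 |
| Tested, inadequate | 20 x 0.309 = 6.2 | 45 x 0.382 = 17.2 |
| Untested, adequate | 2.2 x 0.691 + 77.8 x 0.309 = 25.5 | 55 x 0.618 = 34.0 |
| Untested, inadequate | 2.2 x 0.309 + 77.8 x 0.691 = 54.5 | 55 x 0.382 = 21.0 |

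More men test with inadequate knowledge, but informed testing also rises and uninformed non-testing falls sharply.

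**The mechanical part.** If print equalled counseling (mean 1.0 in both), tested-and-inadequate would still go from 0.20 x 0.309 = 6.2% to 0.45 x 0.309 = 13.9%. ST produces more such men whenever its share of testers below the cut-off exceeds 0.20/0.45 = 0.44 times the UC share.

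**The case against.** The strongest reply is that the comparison is the intended one. ST is a bundle that includes proactive education; UC is a letter with optional counseling; comparing all randomised men is correct, and restricting to testers would break randomisation. Declining is also a decision, and on the illustrated inputs ST leaves more men adequately informed overall. The protocol nowhere claims that print is non-inferior to counseling on knowledge. There are safeguards too: free optional counseling for ST men, counselor disclosure of positive and uncertain results, and a signed laboratory consent. All of this stands.

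A reader might infer that H1.2 could be declared supported while uninformed testing rises, and so that ST does harm. The documents do not support that reading. They give no knowledge distribution, so any such rise is assumed; it looks at one cell of four; and the per-randomised figure grows with uptake even when print teaches as well as counseling. Nor does section 15.1 name uninformed testing as the risk; its discussion closes on psychosocial outcomes.

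Measurement is a further limit. T1 falls 2-3 months after randomisation and may follow disclosure, which is by counselor for all UC results but by letter for ST negatives (section 2.0). T1 knowledge among UC testers may therefore include post-test counseling, which would count against ST.

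What the reply does not meet is the mismatch between the hypothesis in section 2.0 and the analysis in section 17.1.

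**Conclusion.** The point holds as a gap between hypothesis and analysis. H1.2 concerns informed decisions including concordance; the planned regressions compare separate scores, and no other planned analysis joins knowledge or attitude to testing. That rests on the text alone.

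That the knowledge contrast is mainly packet against letter is an inference. It needs a testing rate after counseling above 40% at 20% UC uptake, which fits the high rate section 2.0 describes. The contrast remains a valid comparison of strategies; it is simply not evidence about direct testers relative to counseled testers. The score-based percentages are illustrations from assumed distributions and predict nothing about this trial. The primary outcome and sample size are unaffected.

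**What to change.** In section 17.1, restore the section 2.0 wording of H1.2 and add:

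1. **An informed-choice outcome for every randomised man**: T1 knowledge above a cut-off fixed before unblinded data are seen, and a decision to test or not that agrees with T0 attitude (with its own fixed cut-off). Compare arms by risk difference with 95% CI. State whether risk comprehension is a further condition or stays a separate score.
2. **The four-cell table by arm** (tested or untested, by adequate or inadequate knowledge), with all randomised men as denominator.
3. **The share of testers with inadequate knowledge, by arm, with CI**, labelled descriptive because conditioning on testing breaks randomisation. It belongs beside the table because the per-randomised count rises mechanically with uptake.
4. **Handling of men without T1 data**: section 17.1 assumes 10%, while section 14.3 cites about 15% withdrawal in previous studies.
5. **Interpretation**: T1 knowledge may follow disclosure, which differs by arm, and a mean difference alone is not evidence that print informs as well as counseling.

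Also reconcile the attitude outcome with Table 1, which has attitudes at T0 only.

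The cost is SAP wording and a few tables from data already scheduled. The downsides are one more secondary outcome, a cut-off that must be chosen and justified, an attitude score that predates the education, and modest precision. At 54 per arm the CI half-width is at most 1.96 x sqrt(2 x 0.25/54) = 19 percentage points. The tester shares would rest on about 0.9 x 12 = 11 UC and 0.9 x 27 = 24 ST men, so they should be read as estimates, not tests.
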